##### 3.4.1.2.1.1 Tabulated list of adverse reactions

Adverse reactions reported are listed according to the following frequency:

- Very common: ( $\geq 1/10$ )
- Common: ( $\geq 1/100$  to  $< 1/10$ )
- Uncommon: ( $\geq 1/1,000$  to  $< 1/100$ )
- Rare: ( $\geq 1/10,000$  to  $< 1/1,000$ )

##### Clinical trial data

System Organ Class	Frequency	Adverse reactions
Infections and infestations	Common (1%-10%)	Upper respiratory tract infection
	Uncommon (0.1%-1%)	Otitis media
Blood and lymphatic system disorders	Uncommon (0.1%-1%)	Lymphadenopathy
Immune system disorders	Rare (0.001%-0.1%)	Allergic reactions
Metabolism and nutrition disorders	Uncommon (0.1%-1%)	Anorexia
Psychiatric disorders	Uncommon (0.1%-1%)	Nervousness, abnormal crying, insomnia
Nervous system disorders	Rare (0.001%-0.1%)	Febrile convulsions
Eye disorders	Uncommon (0.1%-1%)	Conjunctivitis
Respiratory, thoracic and mediastinal disorders	Uncommon (0.1%-1%)	Bronchitis, cough
Gastrointestinal disorders	Uncommon (0.1%-1%)	Parotid gland enlargement Diarrhoea Vomiting
Skin and subcutaneous tissue disorders	Common (1%-10%)	Rash
General disorders and administration site conditions	Very common ( $>10\%$ )	Redness at the injection site Fever $\geq 38^{\circ}\text{C}$ (rectal) or $\geq 37.5^{\circ}\text{C}$ (axillary/oral)
	Common (1%-10%) to Very common ( $>10\%$ )*	Pain and swelling at the injection site Fever $>39.5^{\circ}\text{C}$ (rectal) or $>39^{\circ}\text{C}$ (axillary/oral)

\*In general, the frequency category for adverse reactions was similar for the first and second vaccine doses. The exception to this was pain at the injection site which was "Common" after the first vaccine dose and "Very common" after the second vaccine dose.

### Post-marketing data

The following adverse reactions have been identified in rare occasions during post-marketing surveillance. Because they are reported voluntarily from a population of unknown size, a true estimate of frequency cannot be provided.

System Organ Class	Adverse reactions
Infections and infestations	Meningitis Measles-like syndrome Mumps-like syndrome (including orchitis, epididymitis and parotitis)
Blood and lymphatic system disorders	Thrombocytopenia Thrombocytopenic purpura
Immune system disorders	Anaphylactic reactions
Nervous system disorders	Encephalitis* Cerebellitis Cerebellitis-like symptoms (including transient gait disturbance and transient ataxia) Guillain-Barré syndrome Transverse myelitis Peripheral neuritis
Vascular disorders	Vasculitis
Skin and subcutaneous tissue disorders	Erythema multiforme
Musculoskeletal and connective tissue disorders	Arthralgia Arthritis

\* **Encephalitis** has been reported with a frequency below 1 per 10 million doses. The risk of encephalitis following administration of the vaccine is far below the risk of encephalitis caused by natural diseases (measles: 1 in 1000 to 2000 cases; mumps: 2-4 in 1000 cases; rubella: approximately 1 in 6000 cases).

Accidental intravascular administration may give rise to severe reactions or even shock.

#### **3.4.1.2.1.2 Overdose**

Cases of overdose (up to 2 times the recommended dose) have been reported during post-marketing surveillance. No adverse events have been associated to the overdose.

#### **3.4.1.2.2 Data from the Cochrane review** 

##### **3.4.1.2.2.1 Aseptic meningitis**

There is evidence supporting an association between aseptic meningitis and MMR vaccines containing Urabe and Leningrad-Zagreb mumps strains, but **no evidence supporting this association for MMR vaccines containing Jeryl Lynn mumps strains** (rr 1.30, 95% CI 0.66 to 2.56; low certainty evidence).

##### **3.4.1.2.2.2 Febrile seizure**

The analyses provide evidence supporting an association between MMR/MMR+V/MMRV vaccines (Jeryl Lynn strain) and febrile seizures. Febrile seizures normally occur in 2% to 4% of healthy children at least once before the age of 5. The **attributable risk febrile seizures vaccine-induced is estimated to be from 1 per 1700 to 1 per 1150 administered doses.**

##### **3.4.1.2.2.3 Idiopathic thrombocytopenic purpura**

The analyses provide evidence supporting an association between MMR vaccination and idiopathic thrombocytopenic purpura (ITP). However, the risk of ITP after vaccination is smaller than after natural infection with these viruses. After natural infection, ITP occurs in 5 cases per 100,000 (1 case per 20,000) per year. **The attributable risk is estimated about 1 case of ITP per 40,000 administered MMR doses.**

#### 3.4.1.2.2.4 Other

There is no evidence of an association between MMR immunisation and:

- **Encephalitis** or **encephalopathy** (rate ratio 0.90, 95% CI 0.50 to 1.61; 2 observational studies; 1,071,088 children; low certainty evidence)
- **Autistic spectrum disorders** (rate ratio 0.93, 95% CI 0.85 to 1.01; 2 observational studies; 1,194,764 children; moderate certainty).

There is insufficient evidence to determine the association between MMR immunisation and:

[figure not shown]
- **Inflammatory bowel disease** (odds ratio 1.42, 95% CI 0.93 to 2.16; 3 observational studies; 409 cases and 1416 controls; moderate certainty evidence).

Additionally, there is no evidence supporting an association between MMR immunisation and:

- Cognitive delay
- Type 1 diabetes
- Asthma
- Dermatitis/eczema
- Hay fever
- Leukaemia
- Multiple sclerosis
- Gait disturbance
- Bacterial or viral infections.

#### 3.4.2 Safety and immunogenicity of the MMR vaccine before 9 months of age

Traditionally, the MMR vaccine was given as of 12 months of age, an age when passive transplacental transferred maternal antibody has disappeared and can no longer interfere with the vaccine response. Since then, the epidemiology of measles has changed, measles infection has become rarer and most infants are now born to uninfected, vaccinated mothers. Infants born to vaccinated mothers lose their passive immunity approximately 3 months earlier than infants born to mothers who have naturally acquired immunity (Fig 7). **Infants born to vaccinated mothers therefore mount an adequate immune response to the measles vaccine at a younger age.**

In the only systematic review available, the pooled estimated measles seroconversion rate was 76% (95% CI, 71 to 82) after vaccination at 6 months of age. However, this estimation is based on observational studies that took place before the switch from mothers who had naturally acquired immunity to measles-vaccinated mothers, and is therefore unlikely to reflect today's reality.

Importantly, the systematic review did not identify any safety issue with similar profile of adverse events across the ages.

In Switzerland, MMR is already known to be safe and well tolerated in 6-month-old infants; it is already recommended by the Swiss Federal Commission for Vaccination in certain situations such as pre-travel and during outbreaks.

### 3.5 Rationale for the dosage, route, regimen

The dose (0.5 ml) and route (intra-muscular injection) remains unchanged. The only change is the age of administration. With the administration of the first dose of MMR at 6 months of age instead of 9 months of age, it provides a unique 3-month long window during which we can study the differences between the two groups, until the control group receives the MMR vaccine at 9 months of age.

### 3.6 Explanation for choice of comparator (or placebo)

The control group will follow the usual vaccination schedule, with the first dose of MMR given at 9 months of age; they will not receive any intervention at 6 months of age (no placebo injection).

It has been deliberately chosen not to use a placebo to increase acceptability and overall feasibility.

### 3.7 Risks / Benefits

**Safety of MMR vaccine at 6 months of age:** MMR is already known to be safe and well tolerated in 6-month-old infants; it is already recommended by the Swiss Federal Commission for Vaccination in certain situations. This study should therefore be considered as a low-risk study.

**Risk of measles outbreak:** In the eventuality of a measles outbreak, participants will be able to receive MMR vaccine if indicated, as recommended by the Swiss Federal Commission for Vaccination. This is unlikely to happen given the low incidence of measles in this age group in Switzerland (1.16 per 100 000 inhabitants in 2020).

**Benefit of MMR vaccine at 6 months of age:** Infants born to unvaccinated mothers in an under-vaccinated population are at risk of contracting measles even right after birth, and therefore have the highest risk of complications, including subacute sclerosing panencephalitis. Transplacentally transmitted anti-measles antibodies can temporarily protect infants born to vaccinated mothers from measles infection, but their level and sustainability vary. This passive immunity is not sufficient to protect infants throughout their first year of life, and measles vaccination should start as early as possible, especially in areas with endemic measles virus transmission, such as Switzerland. In these regions, the first dose of measles-containing vaccine should be given as early as possible. Lowering the age of the administration of the first dose of measles vaccine is particularly important in the current post-vaccination era. Indeed, the peak concentration of vaccine-induced measles-specific antibody is typically lower than that induced by wild-strain infection. As a result, the antibody concentration in infants born to vaccinated mothers is at least three-fold lower than in infants born to mothers who have naturally acquired immunity.

**Overall benefit of the trial:** this translational trial would be the **first RCT to evaluate the non-specific effects and in-depth immunogenicity of early MMR in a high-income country**, with a comprehensive assessment of both clinical and immunological outcomes, including cell function and memory. It will also be among the first trials of the non-specific effects of vaccines to relate in-vitro findings to clinical outcomes. The robust setting of the study and immune read-outs are expected to provide high value data to confirm preliminary data from previous studies in low-income countries that are often limited by the high rate of missing data and the imprecision of many of the measures. A better understanding of non-specific effects has the potential to provide crucial progress in vaccine research, both for existing and future pathogens. Moreover, vaccination schedules could be easily adapted if early MMR vaccination is proven to have beneficial non-specific effects. **The outcomes of this study will directly inform and benefit vaccination strategies worldwide.**

The study of the non-specific effects of vaccination is an emerging branch in vaccinology and translational research. Improved understanding will have a high impact on immunisation schedules and infant health, as well as expected implications for alternative use of vaccines, for vaccination policies, and for the design of novel immunotherapeutic approaches. Infectious diseases remain a leading cause of morbidity and mortality in children under five years of age worldwide. While the development of pathogen-specific vaccines continues to be one of the pillars of infectious diseases prevention, understanding the beneficial and potential detrimental non-specific effects of vaccines will enable manipulation of these effects to optimise vaccine strategies and improve infant health. Rather than targeting a specific pathogen, "trained immunity-based vaccination" could be designed to provide broader protection by enhancing the innate immune response. In addition, considering the rise in anti-vaccination movements and greater public interest in the effects of vaccines, it is important that both the specific and non-specific effects of vaccines are rigorously investigated and understood. A solid evidence based knowledge is urgently needed to counter potential future vaccine non-compliance resulting from concerns over the use of non-live vaccines.

### 3.8 Justification of choice of study population

The subjects chosen are the target population for the intervention, should the modified schedule show a benefit. As older subjects are unlikely to be MMR-naïve, 6-months-old infant are the population of choice to study the non-specific effects of MMR. Moreover, the clinical significance and duration of non-specific effects of vaccines, as well as the underlying mechanisms, probably differ with age. The immune system is more susceptible to immunomodulation in neonates than in older individuals; for example,

BCG-induced immunological changes differ between neonates, in whom pro-inflammatory cytokine responses to unrelated pathogens were found to be generally reduced, infants, and adults, in whom pro-inflammatory cytokine responses to unrelated pathogens are generally increased. In one RCT lead by our group, the immunological changes measured following neonatal BCG vaccination differed at 7 days, and 7 months of age, within the same cohort of participants.

## 4. STUDY OBJECTIVES

### 4.1 Overall Objective

The aims of the proposed RCT are to determine whether optimising the MMR schedule reduces the burden of disease in childhood (infection with unrelated pathogens and allergic diseases), and to explore the underlying immunological mechanisms that could explain these clinical effects. This study will compare the current Swiss vaccine administration schedule with a modified schedule, designed to maximise the beneficial non-specific effects of MMR.

Two interventions will be assessed in the modified schedule:

**Stage A:** To administer the first dose of MMR at an earlier age

**Stage B:** To administer the second dose of MMR subsequently to (and not concomitantly with) other the non-live vaccines that are planned to be administered at this age (namely diphtheria-tetanus-pertussis-containing vaccine and the pneumococcal vaccine)

The impact of these two interventions will be measured separately and in combination using a factorial design (see Section 6).

### 4.2 Primary Objective

#### Stage A

**AIM1:** Determine whether early MMR vaccination (6 months of age) reduces the number of **respiratory infections** with unrelated pathogens between 6 months and 9 months of age.

*Hypothesis:* Children receiving early MMR are less likely to develop infections between 6 months and 9 months of age because of trained immunity induced by the live-attenuated MMR vaccine, compared to controls who received a non-live vaccine (DTP) as their last vaccination. The difference between the two groups is most likely to be seen for respiratory infections, justifying it to be the primary objective.

### 4.3 Secondary Objectives

#### Clinical objectives

#### Stage A

**AIM1:** Determine whether early MMR vaccination (6 months of age) reduces the number and severity of **infections** with unrelated pathogens between 6 months and 9 months of age.

*Hypothesis:* Children receiving early MMR are less likely to develop infections between 6 months and 9 months of age because of trained immunity induced by the live-attenuated MMR vaccine, compared to controls who received a non-live vaccine (DTP) as their last vaccination. The difference between the two groups is most likely to be seen for respiratory infections, but might as well be observed for other infections, justify them to be included as secondary objectives.

**AIM2:** Determine whether early MMR vaccination (6 months of age) reduces the risk and severity of **atopic and allergic diseases** between 6 months and 9 months of age.

*Hypothesis:* MMR acts as an early-life stimulus and prevents allergy by skewing the developing immune system toward a Th1 response, with corresponding down-regulation of Th2 responses.

#### Stage B

**AIM3:** Determine whether the administration of the second MMR vaccine after the 12-month DTP and

PCV (not simultaneously with) reduces the number and severity of **infections** with unrelated pathogens between 13 months and 24 months of age.

*Hypothesis:* Children receiving MMR on its own (whose last vaccine received is therefore a live-attenuated vaccine) are less likely to develop infection because of trained immunity induced by the MMR vaccine, compared to controls who received non-live vaccine (DTP and/or PCV) simultaneously with MMR as the last vaccine.

**AIM4:** Determine whether administration of the second MMR vaccine after the 12-month DTP and PCV (not simultaneously with) reduces the risk and severity of **atopic and allergic diseases** between 13 months and 24 months of age.

*Hypothesis:* MMR given on its own might be more capable to prevent allergy by modelling the developing immune system toward a Th1 response, and corresponding down-regulation of Th2 responses.

### Stages A and B

**AIM5:** Determine whether one of the two interventions has more impact, or if they are **synergistic**, and evaluate how children, maternal and environmental **factors influence the clinical outcomes**.

*Hypothesis:* The two intervention are synergistic and the non-specific effects observed are modulated by host factors (e.g. sex, ethnicity), exposure (e.g. day-care, siblings, pets, smoking), underlying immunity (e.g. previous infections), and familial history (e.g. allergy).

## Laboratory objectives

### Stages A and B

**AIM6:** Determine the **immunological non-specific** effects of MMR using in-vitro stimulation assays.

*Hypothesis:* MMR induces persistent changes in innate immune cells that modify their responsiveness to unrelated pathogens. The in-vitro immune response to various pathogen-derived triggers differs between the 2 groups, due to vaccine-induced modulation of the immune system.

**AIM7:** Identify the **biological pathways** and molecular mechanisms that underpin non-specific effects of MMR.

*Hypothesis:* Similar to the effects of BCG vaccination in adults, MMR alters infants' innate immunity by inducing epigenetic reprogramming of immune cells (e.g. monocytes) in a process called "trained immunity", associated with altered gene expression and clinical outcome.

**AIM8:** Determine the **immunogenicity** of early MMR vaccination.

*Hypothesis:* MMR vaccine is immunogenic at 6 months of age, inducing high seroprotection rate and memory cells; there is no indication to administer a third dose. As infants born to vaccinated mothers the subjects are more likely to have lost their transplacentally transferred maternal antibodies and are therefore more likely to mount an adequate immune response to the measles vaccine at a younger age.

**AIM9:** Determine whether one of the two interventions has more impact, or if they are **synergistic**, and evaluate how children, maternal and environmental **factors influence the laboratory outcomes**.

*Hypothesis:* The two intervention are synergistic and the non-specific effects observed in blood analysis are also modulated by host factors (e.g. sex, ethnicity), exposure (e.g. day-care, siblings, pets, smoking), underlying immunity (e.g. previous infections), and familial history (e.g. allergy).

## 4.4 Safety Objectives

### Stage A

**AIM10:** Determine the safety of early MMR vaccination.

*Hypothesis:* MMR vaccine is safe and well-tolerated at 6 months of age, inducing similar safety profile than when given later on.

## 5. STUDY OUTCOMES

### 5.1 Primary Outcome

#### Stage A

**AIM1:** Number of parent-reported respiratory infections between 6 months and 9 months of age.

*Justification:* As shown in previous studies on the non-specific effect of vaccines, the difference between the two groups is most likely to be seen for respiratory infections, justifying it to be the primary outcome measure. This outcome measure is also clinically relevant given the high burden of disease attributable to respiratory infections in infants.

### 5.2 Secondary Outcomes

#### Clinical outcomes

##### Stages A and B

**AIM1&3: Infections:** Additional measures of infection, with measurement of the following events: any infection, otitis, upper/lower respiratory tract infection, gastroenteritis, urinary tract infection, osteoarticular infection, and trauma/accident (the latter being used as 'negative control' events), including (i) time to first event, (ii) prevalence, (iii) incidence, (iv) days free of event, (v) severity (duration, antibiotic use, hospitalisation, and outcome) of each event, measured between 6 months and 24 months of life.

*Justification:* The trained immunity induced by MMR vaccination will not only reduce the risk of infection overall, but also decrease their severity

**AIMS2&4: Allergic and atopic diseases:** Eczema, food allergy, and wheezing diseases measured as (i) time to first event/flare, (ii) prevalence, (iii) incidence of event/flaring, (iv) days free of event/flare, (v) severity (scores (see below), treatment, hospitalisation, impact on growth and quality of life) of each event/flare, measured between 6 months and 24 months of life.

*Justification:* The trained immunity induced by MMR vaccination will reduce the risk of developing allergic disease and decrease their severity

**AIM5: Influence of interventions, children, maternal and environmental factors on study outcomes:** Factorial and multivariate analyses will assess the impact of interventions (early MMR, non-concomitant MMR), host factors (e.g. sex, ethnicity), exposure (e.g. day-care, siblings, pets, smoking), underlying immunity (e.g. previous infections), and familial history (e.g. allergy) on clinical outcomes defined above.

*Justification:* Both interventions are expected to have non-specific effects but it is unclear to whether they are synergistic. The other factors listed above are known to possibly influence the non-specific effect of vaccines. Understanding to what extent they influence the non-specific effect of MMR would help identifying subgroup that would benefit the most from a modified vaccination schedule.

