## 9.2.2 Assessment of secondary outcomes

### Clinical outcomes

#### Stages A and B

#### AIM1&3: Infections

*Outcome measure:* Additional measures of infection, with measurement of the following events: any infection, otitis, upper respiratory tract infection, lower respiratory tract infection, gastroenteritis, urinary tract infection, osteoarticular infection, and trauma/accident (the latter being used as control event), including:

- (i) **Time to first event** – Calculated as:  
For participants who have an event:  
*Date of event onset - date of randomisation*  
For participants who did not have an event:  
*Earliest censoring date - date of randomisation*
- (ii) **Prevalence** - Calculated as:  
*number of participants who have an event / total number of participants*
- (iii) **Incidence** - Calculated as:  
*number of events / total time of follow-up*
- (iv) **Days free of event** - Calculated as:  
*number of days free of event / total days of follow-up of participants*
- (v) **Severity of event** – measured as:
  1. **Duration** – Per event, calculated as: *date of recovery - date of onset*
  2. **Antibiotic use** - Per event, including: *yes/no, antibiotic name, dose, route, duration*
  3. **Hospitalisation** - Per event, including: *yes/no, ward/critical care, duration, treatment received*
  4. **Outcome** - Per event, including: *uneventful/complication/sequel/death*

of each category of event, measured between 6 months and 24 months of life, using fortnightly REDCap questionnaires, with validation of data by confirmation with treating paediatrician and medical records.

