### 11.4.3 Secondary Analyses

The socio-demographic and clinical characteristics of the participants will be described using standard descriptive statistics (frequencies, medians and interquartile ranges, or means and standard deviation). Other comparative analyses at the 9-months and 2-years endpoints will be performed using chi-square test (or Fisher's test when appropriate) for categorical variables, and paired t-test or Wilcoxon signed-rank test for continuous variables, depending on the distribution of the variable. Time-to-event outcomes will be assessed using Cox proportional hazards with adjustment for baseline risk factors. Factorial analysis will enable to measure the effect on all outcomes of the intervention made to the first and the second dose of MMR, separately or in combination.

The infection outcomes of the 2-year endpoint will be analysed in two stages:

1) first we will examine the infection count distributions in the 4 experimental conditions: standard schedule (Group C.C.), early first dose (Group M.C.), separated 2nd dose (Group C.M.), both intervention (Group M.M.). We will check if the effects of one intervention appear similar across strata of the other intervention. This will be done to identify strong qualitative interactions (e.g., absence of effect in one stratum versus presence in the other), and to guide the regression models.

2) then we will use negative binomial regression models, starting with a model that includes an interaction term:

$\log(\text{infections}) = b_0 + b_1 \cdot \text{early} + b_2 \cdot \text{separate} + b_3 \cdot \text{early} \cdot \text{separate}$  where "early" and "separate" designate the 2 components of the intervention, both coded as 0 or 1. We will consider the coefficient  $b_3$  to decide on further analysis. If  $b_3$  is of small magnitude (in clinical and scientific terms) we will conclude to the absence of a statistical interaction (on a multiplicative risk scale), and we will drop the interaction term from further analysis. If  $b_3$  is of substantial size, further analysis will proceed as though the trial was a 4-arm trial, with 3 interventions (Group M.C, Group C.M. and Group M.M.) compared to the standard schedule arm (Group C.C.). The assessment of  $b_3$  will be based primarily on scientific and clinical relevance, not on statistical significance.

Model in absence of interaction:

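### Infection severity is defined only per event, so comparing arms on it conditions on having an infection and could mislead if mild infections are prevented more than severe ones

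*Protocol*

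**What the plan says.** Protocol Section 5.2 (AIM1&3) ends its list of infection measures with "severity (duration, antibiotic use, hospitalisation, and outcome) of each event, measured between 6 months and 24 months of life". The justification beneath it reads "The trained immunity induced by MMR vaccination will not only reduce the risk of infection overall, but also decrease their severity", so severity is meant to carry a claim separate from the reduction in number.

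Section 9.2.2 gives the definitions. Duration is "Per event, calculated as" recovery date minus onset date. Antibiotic use, hospitalisation and outcome are each defined per event as well. The neighbouring measures have a different base: prevalence is divided by all participants, and incidence and days free of event by follow-up time.

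Section 11.4.1 promises comparison by intention to treat. Section 11.4.3 assigns the remaining 9-month and 2-year comparisons to chi-square or Fisher tests "for categorical variables, and paired t-test or Wilcoxon signed-rank test for continuous variables". It names no unit of analysis for severity. The negative binomial models in that section are for infection counts.

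**The concern.** An infection occurs after randomisation, and the trial's hypothesis is that the vaccine changes how many occur. Severity averaged over events compares two sets of infections that the vaccine may itself have selected. Randomisation makes the children comparable, not the infections they go on to have.

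The risk is to the direction of the result. If early MMR removes mainly mild infections, those that remain are on average more severe, and a per-event comparison reads this as worse severity although no child is worse off. The stated aim is to reduce both number and severity, so an artefact of this kind would count directly against a beneficial effect.

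Repeated episodes in one child raise a second question. They are correlated, and the protocol does not say how they are handled.

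**Working it through.** **Inputs from protocol Section 11.2:** 0.29 respiratory infections per month (SD 0.32) in controls, 30% reduction, two-sided 5% level, 80% power, 85% completion, 250 against 250 children.

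**Assumptions, not in the documents:** the share of control infections that are severe (10%, 20% and 30% shown); the within-child correlation (0.1 to 0.2); and the 6-9 month rate continuing to 24 months, used only for clustering.

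**The plan's own figure.** Difference 0.29 × 0.30 = 0.087. Per arm, 2 × (1.96 + 0.842)² × 0.32² / 0.087² gives 213. Dividing by 0.85 gives 251, or 502 in total against 500 stated. The sample size reproduces and is not in question.

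**Who enters a per-event comparison at 6-9 months.** The mean count is 0.29 × 3 = 0.87 in controls and 0.87 × 0.70 = 0.609 with early MMR. A negative binomial fitted to mean 0.87 and SD 0.32 × 3 = 0.96 has size 0.87² / (0.9216 − 0.87) = 14.7. Keeping that size in both arms, about 57% of controls and 45% of early-MMR children have at least one infection. That is about 121 and 95 of 212 evaluable children, with 212 × 0.87 = 184 and 212 × 0.609 = 129 events.

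**Severe share per event.** If s is the control share and R the rate ratio for severe infections, the early-MMR share is s × R / 0.70. If only mild infections are prevented, R = 1 and the share is multiplied by 1 / 0.70 = 1.43.

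| Severe share, controls (assumed) | Severe share, early MMR | Severe infections per child, both arms | Chi-square on pooled events significant towards harm |
|---|---|---|---|
| 10% | 14.3% | 0.10 × 0.87 = 0.087 | 21-22% |
| 20% | 28.6% | 0.20 × 0.87 = 0.174 | 42-43% |
| 30% | 42.9% | 0.30 × 0.87 = 0.261 | 65-67% |

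The last column comes from simulations with 212 children per arm (4000 runs; Poisson counts, and for the 10% and 20% rows also the negative binomial above). A normal approximation on 184 and 129 events agrees.

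**Other values of R, total reduction still 30%:**
- Severe infections fall 20%: ratio of shares 0.80 / 0.70 = 1.14, although severe infections per child fall (at s = 10%) from 0.087 to 0.070.
- Severe infections fall 30%: ratio 1.00, no distortion.
- Severe infections fall 50%: ratio 0.50 / 0.70 = 0.71, towards benefit.

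**Repeated episodes.** Over 18 months, 0.29 × 18 = 5.2 events per child. If episodes were pooled as independent, a nominal 5% test would have true size 2 × (1 − Φ(1.96 / √DE)). With DE = 1 + 5.22 × ICC this is 11% at ICC 0.1 and 17% at ICC 0.2. With DE = 1 + 4.22 × ICC it is 10% and 15%.

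**The case against.** The strongest reply is that per event describes how data are recorded, not how arms are compared. Section 11.4 leaves full analysis details to the statistical analysis plan. A reader might infer that the protocol plans a chi-square test on pooled episodes treated as independent. It does not say so, and Section 11.4.3 gives only generic tests. The rejection rates and the 10-17% test size above are therefore conditional on an analysis the protocol does not specify.

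A reader might also infer that a vaccine that prevents infections must look harmful on this scale. That does not follow: the reversal needs mild infections to be prevented proportionally more than severe ones.

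Nor is the all-child picture empty. Section 9.2 lists treatment and hospitalisation among items extractable for each participant. Lower respiratory infection and otitis have their own prevalence and incidence. Days free of event partly covers duration. Admissions are serious adverse events and appear by group in the safety report (Section 11.4.5). These are mitigations, but Section 9.2 fixes no per-child summary, and the safety report is descriptive and not specific to infection.

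Finally, Section 11.4 ties the 5% threshold to the primary outcome only, so no confirmatory claim rests on severity. Over 6-24 months most children would have some respiratory infection (about 1% to 16% of controls event-free, depending on overdispersion, if the rate persists). There the selection is mainly of events; at 6-9 months it is also of children.

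What remains is that the protocol itself fixes the unit. An analysis plan that follows Section 9.2.2 inherits the problem.

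**Conclusion.** The point holds in a limited form. All four infection severity components are defined only per event, so a comparison of arms on them conditions on a post-randomisation event that the vaccine is expected to change. Antibiotic use and infection hospitalisation have no stated measure over all randomised children.

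The per-event result could point to harm with no child worse off. The factor is 1.43 if a 30% reduction is entirely in mild infections, 1.14 if severe infections fall by 20%, and 1.00 under proportional prevention. The factor depends on the 30% reduction and on R; the chance of a significant false signal also depends on the assumed severe share.

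The documents do not support saying that severity will be analysed as pooled independent events, or that the reversal will occur. The handling of repeated episodes is unstated. These are secondary outcomes, and the primary analysis and sample size stand. The change is still worth making, because it removes an avoidable bias at little cost.

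**What to change.** In Sections 5.2 and 9.2.2, define the between-arm severity comparisons per randomised child over follow-up time: antibiotic-treated infections, infection admissions and infection days per child-month, with zero for children who have none. Analyse them by negative binomial regression with a log follow-up offset, the model family already planned for infection counts. Where events are rare, use a per-child yes/no measure or a descriptive summary. Keep the per-event figures, labelled as descriptive, with standard errors clustered by child.

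All items are already collected (Section 9.2, Table 4), so only wording changes. The cost is slightly more analysis work, and per-event severity is no longer a formal comparison.
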